**Table 1: Dose Modification Schedule and Rules Through Study Day 85**

Study Day	Dose and Requirements for Dose Modification
1	Initiate dosing at 5 mg twice daily
15	At Day 15, dose will be increased to 10 mg twice daily if all of the following are true: 
 
• Subject has not achieved and maintained at least Partial Remission and
 
• Subject is not a Treatment Failure
 

29	At Day 29, PK samples will be collected to measure AUC 0-6 and enable projection of AUC 0-12 at both the current dose level and the next higher planned dose level AUC 0-12
43	At Day 43 based on results of the Day 29 PK, the dose may be adjusted to the next higher planned dose level (15 mg twice daily for subjects receiving 10 mg twice daily; 10 mg twice daily for subjects receiving 5 mg twice daily) if all of the following are true: 
 
• Subject is not a Treatment Failure, and
 
• Meets all criteria for continuation:               
 
○ Subject has not achieved and maintained at least a Partial Remission, and
 
○ Projected AUC0-12 on the next higher planned dose level does not exceed 240 <math>\mu\text{g}\cdot\text{h}/\text{mL}</math> and
 
○ The next higher dose does not exceed the Maximum Tolerated Dose (MTD)
 
 
 
 NOTE: If the projected AUC 0-12 on the current dose exceeds 240 $\mu\text{g}\cdot\text{h}/\text{mL}$ , dose will be de-escalated to the next lower dose level
57	At Day 57, PK samples will be collected to measure AUC 0-6 and enable projection of AUC 0-12
Day 71	Based on results of Day 57 PK, subjects can be considered for dose escalation if all of the following are true: 
 
• Subject is not already treated with 15 mg twice daily and
 
• Subject did not require previous downward dose adjustment and
 
• Subject is not a Treatment Failure, and
 
• Meets all criteria for continuation:               
 
○ Subject has not achieved and maintained at least a Partial
 
 
 

	
Remission, and
 
 
○ Projected AUC0-12 on the next higher planned dose level does not exceed 240 <math>\mu\text{g}\cdot\text{h}/\text{mL}</math> and
 
○ The next higher dose does not exceed the Maximum Tolerated Dose (MTD)
 
 
NOTE: If the projected AUC0-12 on the current dose exceeds 240 <math>\mu\text{g}\cdot\text{h}/\text{mL}</math>, dose will be de-escalated to the next lower dose level

Day 85 and beyond	If dose is adjusted upward or downward for any reason at Day 85 or during the extended treatment period the subject will return approximately 2 weeks later for blood draws to assess PK (AUC 0-6 ). Subjects will return 2 weeks after the PK assessment to evaluate the safety and need for further dose adjustment.

Blood will be drawn to evaluate trough exposure in accordance with the Time and Events Schedule. In addition, blood will be drawn to assess exposure (AUC0-12), extrapolated from measured AUC0-6), at the following times to guide dosing decisions:

- Study Day 1 prior to first dose of CCX140, and at intervals through 6 hours following the initial dose
- On study Day 29, two weeks following initiation of 10 mg twice daily, to assess exposure at steady state, and to confirm that exposure is within the safety margins based on non-clinical NOAEL
- If dose was adjusted on Day 43, blood will be collected on study Day 57 to assess AUC0-6
- Additional assessments of exposure may be scheduled if indicated. Indications may include:
  - Subjects receiving a total dose greater than 10 mg daily who have experienced at least 50% reduction in proteinuria since the previous PK assessment, to assess impact of change in proteinuria on exposure and to ensure exposure is within safety margins
  - Subjects who experienced a potentially dose-limiting safety event
  - Subjects who required a dose reduction for higher than planned exposure; PK will be assessed approximately 2 weeks after reduction
  - Subjects for whom dose is adjusted for any other reason; PK will be assessed approximately 2 weeks after reduction

If measured or projected steady state PK exposure (AUC0-12) exceeds 240  $\mu\text{g}\cdot\text{h}/\text{mL}$ , which is approximately half of the rat NOAEL AUC0-24, the dose will be reduced to the dose projected to provide exposure within the target range.

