### Extended Treatment Period

- Subjects are eligible for the extended treatment period under the following conditions:
  1. Not considered treatment failures as of Week 12 *and*
  2. In the opinion of the Investigator, remain candidates for investigational treatment *and*
  3. Any of the conditions below apply:

- Partial or Complete Remission by Week 12
- Response with  $\geq 20\%$  reduction in UPCR by Week 12
- No longer have nephrotic syndrome

These subjects will return to clinic for safety, PK and efficacy measurements every 4-8 weeks. Subjects taking CCX140-B at 15 mg twice daily will be maintained at that dose unless de-escalation is required based on safety signal or steady state PK exposure ( $AUC_{0-12}$ ) exceeds 240  $\mu\text{g}\cdot\text{h}/\text{mL}$ .

Subjects can be considered for dose escalation if all of the following are true:

- Subject is not already treated with 15 mg twice daily and
- Subject did not require previous downward dose adjustment *and*
- Subject is not a Treatment Failure, *and*
- Meets all criteria for continuation:
  - Subject has not achieved and maintained at least a Partial Remission, *and*
  - Projected  $AUC_{0-12}$  on the next higher planned dose level does not exceed 240  $\mu\text{g}\cdot\text{h}/\text{mL}$  *and*
  - The next higher dose does not exceed the Maximum Tolerated Dose (MTD)

Subjects who undergo dose escalation will return to clinic approximately 2 weeks after initiation of the increase for assessment of PK.

Dose modification rules that applied during the initial dose escalation period also apply to dose escalation after 12 weeks.

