### 3.1.3. Follow-Up

Following completion of treatment, or early termination of treatment, all subjects should be urged to return for the termination visit and again 7 and 14 days after their last dose for blood draws to assess elimination pharmacokinetics, and 28 days after their last dose for follow-up and End of Study visit assessments. Appropriate standard of care medical treatment should be provided to all subjects as needed.

After Study Day 43, dose escalation can occur by not more than one step monthly. Within 2 weeks following each dose escalation, PK must be assessed to ensure that the projected AUC0-12 does not exceed 240  $\mu\text{g}\cdot\text{h}/\text{mL}$ . Unscheduled visits for assessment of PK may be required.

Stopping rules and dose reduction rules that applied during the 12 week initial dose escalation period also apply during dose escalation after 12 weeks (See [Table 2](#)).

Throughout the treatment period, any changes in background medications should be limited to settings in which the Investigator deems it to be necessary for the safety of the subject.

Subjects will be discharged from the study when all the visit procedures have been completed.

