## 3.2. Dose Modification Based on PK Exposure

Blood will be drawn to evaluate trough exposure in accordance with the Time and Events Schedule. In addition, blood will be drawn to assess exposure (AUC0-12, extrapolated from measured AUC0-6) at the following times to guide dosing decisions:

- Study Day 1 prior to first dose of CCX140-B, and at intervals through 6 hours following the initial dose
- Two weeks (Day 29) following initiation of 10 mg twice daily, to assess exposure at steady state, and to confirm that exposure is within the safety margins based on non-clinical NOAEL
- Approximately 2 weeks following initiation of 15 mg twice daily (Day 57, if dose was increased at Day 43), to assess exposure at steady state, and to confirm that exposure is

within the safety margins (projected  $AUC_{0-12}$  less than or equal to 240  $\mu\text{g}\cdot\text{h}/\text{mL}$ ) based on non-clinical NOAEL

- At Study Day 85 PK will be assessed to guide dosing beyond Week 12.
- Additional assessments of exposure may be scheduled if indicated. Indications may include:
  - Subjects receiving a total dose greater than 10 mg daily who have experienced at least 50% reduction in proteinuria since the previous PK assessment, to assess impact of change in proteinuria on exposure and to ensure exposure is within safety margins
  - Subjects who experienced a potentially dose-limiting safety event
  - Subjects who required a dose reduction for higher than planned exposure; PK will be assessed approximately 2 weeks after reduction
  - Subjects for whom dose is adjusted for any other reason; PK will be assessed approximately 2 weeks after reduction

If planned dose escalation to 10 mg (on day 15) or 15 mg twice daily (on day 43) was previously halted the dose may be escalated further if subjects are not considered treatment failures and otherwise meet criteria for continuation ([Table 1](#), [Figure 1](#)). In such cases the subject will return approximately 2 weeks later for blood draws to assess PK ( $AUC_{0-6}$ ). Subjects will return 2 weeks after the PK assessment to evaluate the safety and need for further dose adjustment.

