### **3.3. Dose Modifications During the Extended Treatment Period**

If measured or projected exposure steady state PK exposure ( $AUC_{0-12}$ ) exceeds 240  $\mu\text{g}\cdot\text{h}/\text{mL}$ , which is approximately half of the rat NOAEL  $AUC_{0-24}$ , the dose will be reduced to the dose projected to provide exposure within the target range.

For subjects who escalate dose to 10 mg twice daily on Study Day 15, PK samples from the dose two weeks after 10 mg BID dosing (planned for Day 29) will be analyzed expeditiously and the PK data will be used for projecting the steady state PK exposure. If the projected steady state PK exposure ( $AUC_{0-12}$ ) is higher than 240  $\mu\text{g}\cdot\text{h}/\text{mL}$ , which is half of the rat NOAEL steady state  $AUC_{0-24}$ , the dose will be reduced to 5 mg BID for the remainder of the study ([Table 2](#)).

If the projected steady state PK exposure ( $AUC_{0-12}$ ) is lower than 240  $\mu\text{g}\cdot\text{h}/\text{mL}$ , the steady PK exposure at 15 mg BID will be projected from the 10 mg BID Day 43 PK data. If the projected PK exposure ( $AUC_{0-12}$ ) at 15 BID is lower than 240  $\mu\text{g}\cdot\text{h}/\text{mL}$ , the dose will be escalated to 15 BID. If the projected PK exposure ( $AUC_{0-12}$ ) is higher than 240  $\mu\text{g}\cdot\text{h}/\text{mL}$ , the dose will not escalate to 15 mg BID but will stay at 10 mg BID for the remainder of the study.

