### 5.2. Rationale for Dose Range

#### 5.2.1. Safety

The three active treatment doses proposed for the study are 5 mg administered twice daily, 10 mg administered twice daily and 15 mg administered twice daily.

Five (5) mg twice daily is selected as the lowest dose for exploration of dose response. The projected exposure at this dose is well below the NOAEL established in non-clinical toxicology studies. Specifically, using the rat as the more sensitive species based on exposure, the NOAEL in the 26-week rat study was 15 mg/kg/day. The NOAEL in the 13-week and 26-week rat studies were associated with systemic exposures to CCX140 which were about 18-20 times higher than the projected human exposure associated with a daily 5 mg dose, and about 8-10 fold a 10 mg BID dose.

Ten (10) mg twice daily is selected as an intermediate dose for exploration of dose response and to guard against losing the efficacious dose if 15 mg twice daily is associated with unexpected or intolerable toxicity. Using the rat as the more sensitive species based on exposure, the NOAEL in the 26-week rat study was 15 mg/kg/day. The NOAEL in the 13-week and 26-week rat studies were associated with systemic exposures to CCX140 which were about 9-10 times higher than the human exposure associated with a daily 10 mg dose, and about 4-5 fold a 10 mg BID dose.

Fifteen (15) mg twice daily is selected as the highest dose for this protocol, which is projected to provide exposure at both peak and trough that is within the safety margins established in the toxicology program, and that is projected to maintain a high level of target engagement, as summarized below and detailed in the Investigator's Brochure. The projected clinical exposure with 15 mg twice daily dosing is 3-fold below the NOAEL exposure established in the most sensitive species tested in the nonclinical toxicity studies (rat 26-week, PO, QD) The safety margin associated with this exposure is approximately 3-fold below the NOAEL established in rat, and 5-8-fold below the exposure established in dog.

The projected exposures and safety margins were established for humans without proteinuria. Because CCX140-B is highly protein bound, nephrotic subjects may have a lower exposure at a given dose due to potential drug loss with protein in urine.

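### At Day 71, two exposure-reduction rules with the same trigger give different doses for a subject on 15 mg BID with AUC0-12 above 360 and up to 720 µg·h/mL

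*Protocol*

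**What the plan says.** The planned doses are 5, 10 and 15 mg BID (protocol Section 5.2.1), and AUC0-12 is capped at 240 µg·h/mL. Two instructions apply once the cap is exceeded:

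- **Step rule.** The Day 43 and Day 71 notes in Table 1 apply when projected AUC0-12 on the current dose is above 240. In that case the "dose will be de-escalated to the next lower dose level".
- **Endpoint rule.** The paragraph after Table 1 applies when measured or projected steady-state AUC0-12 is above 240. In that case "the dose will be reduced to the dose projected to provide exposure within the target range". Sections 3.1 and 3.3 repeat it.

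The term target range has no definition of its own. Section 3.2 describes exposure within the safety margins as projected AUC0-12 "less than or equal to 240" µg·h/mL, which is a reasonable upper bound for it. Section 3.3 also sets one specific move: a subject on 10 mg BID projected above 240 has a reduction in which "the dose will be reduced to 5 mg BID for the remainder of the study". The SAP schematic (Section 2.2.1) lists AUC0-12 above 240 as a reason to de-escalate but gives no step size. Neither document ranks the two rules.

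**The concern.** The step rule fixes how far the dose falls and the endpoint rule fixes where exposure must end up. They agree whenever one step is enough. When one step is not enough, the Day 71 note sends the subject to a dose that the PK result in hand already places above the cap, and two sites could treat the same result differently.

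The cap has little slack. It applies to 12 hours, so at steady state on BID dosing it corresponds to 2 × 240 = 480 µg·h/mL per day. Section 1.3 gives the rat NOAEL AUC0-24 as 464.6 (males) and 493.7 (females). A dose projected above the cap is therefore around or above the full daily NOAEL exposure. The finding behind that NOAEL is reversible anemia, which the protocol considers likely to carry over to humans.

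**Working it through.** **Inputs**
- Cap: AUC0-12 of 240 µg·h/mL (Table 1; Section 3.2).
- Projected AUC0-12 at 15 mg BID: 72 (Synopsis, Rationale for Dose Range).
- Planned levels: 5, 10 and 15 mg BID (Section 5.2.1).
- Entry to 15 mg BID requires a projected AUC0-12 of no more than 240 (Table 1).

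**The plan's own figure.** The cap is described as about half the rat NOAEL AUC0-24. Half of 464.6 is 232.3, half of 493.7 is 246.9, and half of the average of the two sexes is 239.6. The figure of 240 is reproduced.

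**Is proportionality reasonable?** The protocol does not state it, but two figures in Section 5.2.1 point to it. The rat margin is 18–20 at 5 mg daily and 9–10 at 10 mg daily, a ratio of 18/9 = 20/10 = 2.0 for a doubled dose. Exposure at 15 mg BID is put at 3.07 times that at 10 mg daily, for a 3-fold daily dose: 3.07/3 = 1.02. The second is only a rough check, because it compares a projection without proteinuria with observations in diabetic nephropathy.

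**Thresholds.** With AUC(d) = A × d/15 for a subject measured at A on 15 mg BID:
- 10 mg BID is above the cap when A > 240 × 15/10 = 360.
- 5 mg BID is above the cap when A > 240 × 15/5 = 720.

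In the table, the endpoint rule is taken to pick the highest planned dose projected at or below 240.

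| A on 15 mg BID | 10 mg BID | 5 mg BID | Day 71 note | Endpoint rule |
|---|---|---|---|---|
| 300 | 200 | 100 | 10 mg | 10 mg |
| 360 | 240 | 120 | 10 mg | 10 mg |
| 400 | 266.7 | 133.3 | 10 mg | 5 mg |
| 500 | 333.3 | 166.7 | 10 mg | 5 mg |
| 720 | 480 | 240 | 10 mg | 5 mg |
| 800 | 533.3 | 266.7 | 10 mg | no planned dose |

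**Sensitivity.** If exposure follows dose^b, the thresholds become 240 × 1.5^b and 240 × 3^b. For b = ln 3.07/ln 3 = 1.021 they are 363 and 737. For b from 0.9 to 1.1 they are 346–375 and 645–804.

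**Where it can arise.** It cannot arise at the Day 43 note. 15 mg BID is first given on Day 43, and from 10 mg BID both rules lead to 5 mg BID up to 240 × 10/5 = 480, above which no planned dose fits. It can arise at Day 71, which acts on the Day 57 PK result.

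**How rare.** 360/72 = 5 times the projected exposure. Relative to the largest projection that would have allowed escalation, 360/240 = 1.5, so exposure must come out more than 1.5 times that projection.

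**The case against.** The best reply is that the two sentences work together: the note sets the step, the paragraph sets the endpoint, and the dose is lowered until the projection is at or below 240. That reading is plausible and leads to a safe dose. But the protocol never says it, and for these subjects the two sentences name different doses from the same result.

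The second reply is remoteness, and it largely stands. The quantified mechanism for a shift in exposure is proteinuria lowering it by about 30% (about 0.8 against 1.2 µg/mL in diabetic nephropathy; Section 5.2.2). Full reversal is a factor of 1/0.7 = 1.43, or 1.2/0.8 = 1.5. From the highest admissible projection of 240 that gives 343 to 360, which does not pass 360. Strong CYP3A4 inhibitors are excluded. Section 3.1 does expect exposure to move with proteinuria, so the case is unlikely but not impossible.

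Third, there are safeguards. Section 3.2 says that after a reduction "PK will be assessed approximately 2 weeks after reduction", Section 3.1 allows de-escalation at any time, and the Safety Review Committee includes a Clinical Pharmacologist (Section 7.5.1). These limit harm, with two reservations. The recheck is listed among assessments that may be scheduled. In addition, Day 85, two weeks after a Day 71 reduction, calls only for a trough sample unless the dose was increased (Section 6.8).

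A reader might infer that the conflict runs through the whole extension, because Section 3.1.3 says "Stopping rules and dose reduction rules that applied during the 12 week initial dose escalation period also apply during dose escalation after 12 weeks" and the synopsis says "Dose modification rules that applied during the initial dose escalation period also apply to dose escalation after 12 weeks". The documents do not clearly support this. Section 3.1.3 points to Table 2, which has no exposure row. The synopsis sentence concerns escalation. Table 1's row for Day 85 onward has no one-step note, and Section 3.3, which is headed for the extension, states the endpoint rule.

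**Conclusion.** The inconsistency is real but minor, and its clear form is confined to the Day 71 note. Under roughly dose-proportional exposure, a subject on 15 mg BID with AUC0-12 above 360 and up to 720 gets 10 mg BID under the note (projected above 240, up to 480) and 5 mg BID under the paragraph (projected above 120, up to 240). The thresholds rest on proportionality, which the protocol's figures imply but do not state; modest departures move them little. At most 13 subjects were planned, and SAP Section 1 records that enrolment was not continued. The statistical analysis is unaffected.

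Three stronger conclusions are not supported:
- **That the endpoint rule is unusable because target range is undefined.** Section 3.2 supplies an upper bound, and a rule for over-exposure needs no lower one.
- **That the missing instruction to hold or stop when 5 mg BID exceeds 240 is an error in its own right.** Section 5.2.1 says "Five (5) mg twice daily is selected as the lowest dose for exploration of dose response", and no passage gives an explicit hold. But proportional scaling puts expected AUC0-12 at 5 mg BID at 72/3 = 24, so this needs 240/24 = 10 times expectation, and general downward adjustment for excess exposure is allowed. It is missing detail.
- **That the Table 2 reference in Section 3.3 sends readers to a different rule.** The amendment summary shows that a duplicate of Table 1, then numbered Table 2, was deleted and the former Table 3 renumbered. The reference is most plausibly a leftover.

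**What to change.** In the Day 43 and Day 71 notes of Table 1, replace the one-step instruction with: reduce to the highest planned dose level with projected AUC0-12 at or below 240 µg·h/mL, and interrupt CCX140-B if none qualifies. Use the same sentence in place of the target-range wording after Table 1 and in Sections 3.1 and 3.3.

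As secondary tidying in Section 3.3, make the move to 5 mg BID subject to the same limit and point to Table 1 instead of Table 2.

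The cost is a protocol clarification of a few sentences, with no added visits, samples or SAP changes. Because enrolment was not continued, its practical reach in this study is very small.

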### Extended Treatment Period

- Subjects are eligible for the extended treatment period under the following conditions:
  1. Not considered treatment failures as of Week 12 *and*
  2. In the opinion of the Investigator, remain candidates for investigational treatment *and*
  3. Any of the conditions below apply:

- Partial or Complete Remission by Week 12
- Response with  $\geq 20\%$  reduction in UPCR by Week 12
- No longer have nephrotic syndrome

These subjects will return to clinic for safety, PK and efficacy measurements every 4-8 weeks. Subjects taking CCX140-B at 15 mg twice daily will be maintained at that dose unless de-escalation is required based on safety signal or steady state PK exposure ( $AUC_{0-12}$ ) exceeds 240  $\mu\text{g}\cdot\text{h}/\text{mL}$ .

Subjects can be considered for dose escalation if all of the following are true:

- Subject is not already treated with 15 mg twice daily and
- Subject did not require previous downward dose adjustment *and*
- Subject is not a Treatment Failure, *and*
- Meets all criteria for continuation:
  - Subject has not achieved and maintained at least a Partial Remission, *and*
  - Projected  $AUC_{0-12}$  on the next higher planned dose level does not exceed 240  $\mu\text{g}\cdot\text{h}/\text{mL}$  *and*
  - The next higher dose does not exceed the Maximum Tolerated Dose (MTD)

Subjects who undergo dose escalation will return to clinic approximately 2 weeks after initiation of the increase for assessment of PK.

Dose modification rules that applied during the initial dose escalation period also apply to dose escalation after 12 weeks.

### **Follow-Up**

Following completion of treatment or early termination of treatment all subjects should be encouraged to return for the termination visit, and 7 and 14 days after their last dose for blood draws to assess elimination pharmacokinetics, and 28 days after their last dose for follow-up and End of Study visit assessments. The subject's condition will be evaluated by the Investigator at the end of study drug administration and again during the post 4 week follow-up visit. Appropriate standard of care medical treatment should be provided to all subjects as needed.

Subjects will be discharged from the study when all the visit procedures have been completed.

